## 2.4 SCIENTIFIC BACKGROUND

Acute kidney injury (AKI) is a serious complication that is independently associated with poor outcomes [1, 2]. Approximately one in five patients with non-severe sepsis develops AKI [3], which increases to two-thirds in critically ill patients. About 50% of ICU patients with AKI die (4-12), and those who survive an episode of AKI have a higher risk of progressing to chronic kidney disease (CKD). Currently, there are few pharmacological therapeutic options available to prevent or treat AKI, and management is limited to alleviating hemodynamic and toxic renal lesions. support measures, such as dialysis.

Iron deficiency occurs in up to 30% of hospitalized patients and has been linked to worse clinical evolution, even in the absence of anemia. This iron deficiency is worse even when anemia figures are reached. It has been documented that critically ill patients develop anemia as part of the process of their pathology. It has been seen that during processes of exacerbation of pathologies such as heart failure, the administration of intravenous iron avoids the probability of hospitalization and clinical evolution (13-16). It has been shown that in DRA there is mitochondrial dysfunction (17), specifically in the renal tubule where the greatest amount of mitochondria is concentrated,

Version 2.0, 29 June 2023

Effect of intravenous iron repletion on renal function in patients with iron deficiency and acute kidney injury, clinical trial. June 2023, HCG/CEI-1232/22

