### 2.5 OBJECTIVES

#### **Primary objective:**

The endpoint of interest was the proportion of patients meeting one or more criteria for Major Adverse Kidney Events within 30 days (MAKE30): in-hospital mortality; receipt of new RRT; or persistent renal dysfunction.

In hospital mortality was defined as death from any cause prior to hospital discharge censored at 30 days after ICU admission. Receipt of new RRT was defined as receipt of any modality of RRT between ICU admission and the first of (1) hospital discharge or (2) 30 days in a patient not known to have received RRT prior to ICU admission. Persistent renal dysfunction was defined as a final serum creatinine value before hospital discharge (censored at 30 days after enrollment) that was  $\geq 200\%$  of the baseline creatinine value.

And will be evaluated at 60 and 90 days.

**Secondary objectives:** all the following will be at hospital discharge and 28 days after hospital discharge between the intervention group (iron replacement) compared to the control group (placebo).

- ferritin value, (pg/dL)
- transferrin saturation (%)
- Hemoglobin (g/dL)
- serum creatinine (mg/dL)
- start of renal support therapy (any type of renal support such as: intermittent hemodialysis, peritoneal dialysis or continuous therapies)
- recovery of renal function, considered as a decrease in serum creatinine and approaching  $<0.3\text{mg/dL}$  of basal creatinine
- death

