## 2. DESIGN OF THE STUDY

Randomized placebo-controlled clinical trial, randomization method in blocks of 5 by frequency of occurrence. In patients with acute kidney injury, they will be randomized to receive the administration of intravenous iron dextran in a single exhibition according to the Mg provided by the Virizzi formula compared to placebo.

The sample size determined 55 patients per group, with a standard deviation of 1.5.

$$n = [(Z_{\alpha/2} + Z_{\beta})^2 \times \{2(\sigma)^2\}] / (\mu_1 - \mu_2)^2$$
$$n = [(1.96 + 0.84)^2 \times \{2(1.5)^2\}] / (10.8 - 10)^2$$
$$n = 55,125$$

n = sample size required in each group  $\mu_1 - \mu_2 =$   
clinically significant difference = 0.8 or = standard  
deviation = 1.5

$Z_{\alpha/2}$ : 1.96

$Z_{\beta}$ : 0.84

Version 2.0, 29 June 2023

Effect of intravenous iron repletion on renal function in patients with iron deficiency and acute kidney injury, clinical trial. June 2023, HCG/CEI-1232/22

[name] [contact], [name] GUADALAJARA, JAL

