### 4.1 INCLUSION AND EXCLUSION CRITERIA

#### criteria of **inclusion**:

Hospitalized patients with ARD, will be defined as the diagnosis using the KDIGO criteria of serum creatinine (Cr); Patients with AKI  $> 18$  and  $< 85$  years, baseline creatinine  $< 2$  mg/dL and with written informed consent will be included.

Iron deficiency according to the criteria of the 2: serum iron  $< 13$  ng/dL, transferrin saturation  $< 20\%$ .

Version 2.0, 29 June 2023

Effect of intravenous iron repletion on renal function in patients with iron deficiency and acute kidney injury, clinical trial. June 2023, HCG/CEI-1232/22

[name] [contact], [name] GUADALAJARA, JAL

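### The secondary renal recovery outcome rests on serum creatinine alone, so a patient still on dialysis can count as recovered, which usually shrinks any difference between arms

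*Protocol*

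**What the plan says.** Protocol section 2.5 (Objectives) gives the secondary outcomes one common timing: "all the following will be at hospital discharge and 28 days after hospital discharge". One of them is "recovery of renal function, considered as a decrease in serum creatinine and approaching" less than 0.3 mg/dL of basal creatinine. I read this as a fall to within 0.3 mg/dL of the basal value. Creatinine is the only variable in the rule.

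Renal support is a separate item in the same list, "start of renal support therapy (any type of renal support such as: intermittent hemodialysis, peritoneal dialysis or continuous therapies"), and death is another. Neither is tied to the recovery rule.

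The primary composite in the same section, MAKE30, treats them differently. Its events are "in-hospital mortality; receipt of new RRT; or persistent renal dysfunction".

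The statistical paragraph in the design section says only that proportions are compared by a chi-square or exact test. Section 4.2 names eGFR and renal function as dependent variables. Neither adds a condition on renal support.

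**The concern.** Dialysis removes creatinine from the blood, so a low value in a dialysed patient does not show that the kidney is working. The protocol expects such patients: section 2.4 names "support measures, such as dialysis" as part of current management. Applied as written, the rule classes some patients who still depend on dialysis as recovered.

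The error would be harmless if it fell equally on both arms. It follows ongoing RRT, however, which is an outcome that iron might change. If iron leaves fewer patients on RRT, placebo is credited with more false recoveries. At stake is the one secondary outcome that the protocol names as recovery, and so part of the evidence for the section 2.6 hypothesis that iron improves renal function.

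**Working it through.** **The plan's own figure.** The only calculation in the protocol is the sample size: (1.96 + 0.84)² × 2 × 1.5² / 0.8² = 7.84 × 4.5 / 0.64 = 55.125, which matches "The sample size determined 55 patients per group, with a standard deviation of 1.5". It concerns a difference of 0.8 in a continuous variable. It says nothing about recovery, and the protocol gives no recovery or RRT rate. All rates below are therefore assumptions.

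**Inputs**
- r1, r0: share of iron and placebo patients still on RRT at the time point (assumed). This is ongoing RRT, not ever having received it.
- s: share of patients off RRT who meet the creatinine rule, equal in both arms (assumed 60%).
- g: share of patients on RRT who meet the creatinine rule (assumed, varied).

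**Formulas**
- True recovery in an arm (off RRT and meeting the rule) = (1 − r) × s
- Measured recovery = (1 − r) × s + r × g
- True difference, iron minus placebo = (r0 − r1) × s
- Measured difference = (r0 − r1) × (s − g)

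The measured difference is the true one multiplied by (1 − g/s). The bias is −g × (r0 − r1), always against the arm with less ongoing RRT.

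**Ongoing RRT 25% placebo v 15% iron, s = 60%.** True recovery is 0.85 × 0.6 = 51% on iron and 0.75 × 0.6 = 45% on placebo, a difference of 6 points.

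| g | Iron, measured | Placebo, measured | Difference (points) |
|---|---|---|---|
| 10% | 51 + 1.5 = 52.5% | 45 + 2.5 = 47.5% | 5 |
| 30% | 51 + 4.5 = 55.5% | 45 + 7.5 = 52.5% | 3 |
| 50% | 51 + 7.5 = 58.5% | 45 + 12.5 = 57.5% | 1 |
| 70% | 51 + 10.5 = 61.5% | 45 + 17.5 = 62.5% | −1 |

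**A wider gap, 30% v 15%, s = 60%.** The true difference is 0.15 × 0.6 = 9 points. Measured: 0.15 × (0.6 − 0.3) = 4.5 points at g = 30%, 1.5 at g = 50%, and −1.5 at g = 70%.

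**A second set of assumptions, with deaths held equal.** Take 20% dead in each arm and counted as not recovered, 10% (iron) v 30% (placebo) of survivors on RRT, and s = 50%. True recovery among all randomised is 0.8 × 0.9 × 0.5 = 36% v 0.8 × 0.7 × 0.5 = 28%, a difference of 8 points. The measured difference is 0.8 × 0.2 × (0.5 − g): 3.2 points at g = 30%, 0 at g = 50%, and −4.8 at g = 80%.

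Both sets show the same pattern. Any g above zero shrinks the difference. The sign changes only when g exceeds s.

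**The case against.** Several points on the other side are sound.

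- **The primary outcome is protected.** MAKE30 counts death and new RRT as events. Both are also reported separately as secondary outcomes, so a reader could see an RRT imbalance beside the recovery result. This stands, although seeing the imbalance does not correct the recovery comparison.
- **Being an event in MAKE30 and a recovery here is not in itself a contradiction.** A patient who was dialysed, came off it and regained near-basal creatinine belongs in both. Only patients still on support at the time point can be misclassified, so r must be ongoing RRT, and g may be low. With a 10-point gap and g = 10%, the bias is 0.1 × 0.1 = 1 point.
- **A reader might infer that the rule is likely to reverse a real effect.** Nothing in the protocol supports that. With equal recovery off RRT, reversal needs dialysed patients to meet the creatinine rule more often than undialysed ones.
- **A reader might infer that patients who die drop out of the denominator.** The protocol does not say so. It gives the dead no recovery status, and counting them as not recovered fits the text equally well. An analysis plan that is not shown may settle this. The section 2.4 figure, "About 50% of ICU patients with AKI die (4-12"), concerns ICU patients, whereas section 4.1 admits hospitalised patients generally.
- **A reader might call this the trial's only measure of renal recovery.** It is not. Persistent renal dysfunction is in the primary composite, and serum creatinine is a secondary outcome of its own.
- **Precision is low under either definition.** Near 50% recovery with 55 per arm, the 95% half-width is 1.96 × √(2 × 0.25 / 55) ≈ 0.187, about 19 points. True differences of 6 or 9 points would not be distinguished from zero anyway. This limits the practical effect on a significance test, but the estimate would still be biased.

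None of this removes the fault. It lies in a definition that the protocol fixes, not in a detail left for later.

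**Conclusion.** The point holds for patients still on renal support. The recovery rule as written can class them as recovered, and nothing else in the protocol prevents it. If ongoing RRT differs by arm, the comparison is biased by g times the RRT gap, usually towards no difference. At 25% v 15% ongoing RRT and 60% recovery off RRT, a true 6 points becomes 3 if 30% of patients on RRT meet the rule and 1 if 50% do.

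These sizes rest wholly on assumed rates and on equal recovery off RRT in the two arms. The supportable claim is attenuation, not a predicted reversal. The protocol's silence on deaths is not counted as an error. This is a flaw in one secondary outcome that should be corrected, and it leaves the primary result intact.

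**What to change.** In section 2.5, define recovery at each time point as all three of the following:
- alive;
- free of renal support for a pre-stated interval before the creatinine sample;
- creatinine within 0.3 mg/dL of basal.

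Count patients who have died or are still on renal support as not recovered, and use all randomised patients as the denominator.

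The interval is needed because a patient on intermittent haemodialysis, sampled between sessions, could otherwise pass as free of support. Its length is for the investigators to set. The change concerns the outcome definition only and alters no treatment.

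The cost is one sentence in the definition and one data field for RRT status at each time point, since the protocol lists the start of support rather than its status at discharge and 28 days later. The reported recovery proportion will be slightly lower.

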#### **Exploratory objectives:**

- safety of intravenous iron administration compared to placebo: assessed by the occurrence of adverse events such as allergic reaction, hypotension, dyspnea, rash, erythema. These will be evaluated during

[name] [contact], [name] GUADALAJARA, JAL

## *Old Civil Hospital of Guadalajara* "FRAY ANTONIO MAYOR"

---

drug administration and during hospitalization frequently every 24 hours by the nephrology staff, including the study investigators.

Version 2.0, 29 June 2023

Effect of intravenous iron repletion on renal function in patients with iron deficiency and acute kidney injury, clinical trial. June 2023, HCG/CEI-1232/22

[name] [contact], [name] GUADALAJARA, JAL

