### 2.1 PROJECT SUMMARY

The purpose of this clinical trial is to carry out research on the effect on hemoglobin and renal function of the intravenous administration of iron dextran as a repletion strategy in patients with iron deficiency anemia and acute kidney injury, in which the patient You may benefit from this medication since it is expected to correct anemia, iron deficiency and renal function parameters, when compared with a control group (placebo), the safety of the drug will also be evaluated by recording adverse effects. I will point out with the patient the risks and benefits of including her in this type of study and I will answer all the doubts that arise, and I will also immediately report any serious adverse effect to the research ethics committee.

Version 2.0, 29 June 2023

Effect of intravenous iron repletion on renal function in patients with iron deficiency and acute kidney injury, clinical trial. June 2023, HCG/CEI-1232/22

[name] [contact], [name] GUADALAJARA, JAL

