## 2.6 HYPOTHESIS

Our hypothesis is that intravenous iron dextran repletion during the treatment of acute kidney injury will improve renal function parameters, iron deficiency, anemia, and also that it will be safe compared to placebo.

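### Adverse events are evaluated only up to hospital discharge, while the hypothesis claims safety against placebo with no such limit

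*Protocol*

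**What the plan says.** In section 2.5, safety is an exploratory objective, "assessed by the occurrence of adverse events such as allergic reaction, hypotension, dyspnea, rash, erythema". The sentence that follows runs over a page break and places the evaluation during "drug administration and during hospitalization frequently every 24 hours by the nephrology staff, including the study investigators". It gives no fixed number of days and no evaluation after discharge.

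The same section plans later follow-up for other purposes. For the secondary objectives, "all the following will be at hospital discharge and 28 days after hospital discharge"; that list includes serum creatinine, start of renal support and death. Of the primary endpoint it says "And will be evaluated at 60 and 90 days".

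Section 2.6 makes safety part of the hypothesis: "and also that it will be safe compared to placebo". Section 2.1 says that "the safety of the drug will also be evaluated by recording adverse effects" and undertakes to report serious adverse effects to the ethics committee at once. Neither statement in 2.1 gives a period. The statistical paragraph at the end of the design section compares categorical variables as proportions, by a chi-square or exact test.

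**The concern.** The safety claim is wider than the data collection behind it.

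- **Late events.** Patients are assessed 28 days after discharge, but the protocol does not ask for adverse events then. A non-serious event that first appears at home is not routinely sought in either arm. No analysis plan can recover what was never asked about, so this is a matter for the protocol.
- **Unequal observation time.** The length of the window is the patient's stay. Stay can depend on renal recovery and on death, which the trial itself compares between arms. If stay differs by arm, a crude comparison of proportions sets unequal observation periods against each other.

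At stake is whether a statement that iron is safe relative to placebo could be read as covering anything beyond the hospital stay.

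**Working it through.** The protocol gives no figure for safety to reproduce. Its one calculation, (1.96 + 0.84)² × 2 × 1.5² / 0.8² = 55.125 per group, concerns a difference of 0.8 between two means and has no bearing on adverse events. The check is therefore mainly one of text, with two illustrations on assumed inputs.

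**Step 1: the passages side by side.**
- Adverse events (2.5, exploratory): administration and hospital stay.
- Secondary outcomes (2.5): discharge and 28 days after discharge.
- Primary endpoint (2.5): 30 days, then days 60 and 90.
- Safety hypothesis (2.6): no time limit.
- Recording of adverse effects and reporting of serious ones (2.1): no time limit, and no post-discharge enquiry described.

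The first item ends earliest, and it is the one on which the safety hypothesis rests.

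**Step 2: how much of the follow-up is covered.** The protocol states no length of stay, so take L days from administration to discharge over an assumed range of 5 to 30. The share of the time to the post-discharge assessment is L / (L + 28); the share of 90 days is L / 90.

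| L (days) | L / (L + 28) | L / 90 |
|---|---|---|
| 5 | 5/33 = 15% | 6% |
| 7 | 7/35 = 20% | 8% |
| 10 | 10/38 = 26% | 11% |
| 14 | 14/42 = 33% | 16% |
| 21 | 21/49 = 43% | 23% |
| 30 | 30/58 = 52% | 33% |

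**Step 3: what unequal stays would do.** Assume the same daily event probability r in both arms, so there is no true difference. The proportion with at least one recorded event is 1 − (1 − r)^L.
- r = 1%, stays of 7 and 10 days: 1 − 0.99⁷ = 6.8% and 1 − 0.99¹⁰ = 9.6%; ratio 0.71.
- r = 2%, same stays: 1 − 0.98⁷ = 13.2% and 1 − 0.98¹⁰ = 18.3%; ratio 0.72.
- Equal stays, any r: ratio 1.0.
- Events confined to the infusion: the proportion does not depend on L, and the ratio is again 1.0.

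The distortion thus needs two things together: stays that differ by arm, and events that accrue over the stay. The protocol gives information on neither.

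**Step 4: whether the existing contact can close the gap.** For a patient discharged L days after first administration, the post-discharge assessment falls on day L + 28. This is never earlier than day 28 from administration, so a window through day 28 is complete at that contact for every patient discharged alive who attends.

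**The case against.** The strongest reply is that safety is exploratory, with no margin and no sample size behind it, and that describing in-hospital tolerability is a reasonable choice at that level. That is fair. It limits the weight of the point, and it means that a reader should not take the hypothesis as a formal test of safety. It does not remove the mismatch, because section 2.6 carries no such limit.

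Three stronger readings are tempting, and the protocol does not support them.

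- **That only infusion reactions are collected.** The five named events are introduced as examples and are checked daily through the stay. Other events are not excluded.
- **That no harm after discharge is seen.** Death, start of renal support and creatinine are taken 28 days after discharge, by arm. The undertaking on serious adverse effects has no end date, so it neither clearly extends the window nor closes it. What remains unsought is other adverse events with onset after discharge.
- **That the comparison is biased, or that one arm will look about 30% safer.** That follows only if stays differ by arm and events accrue steadily. The daily rate and the 3-day difference in stay are assumptions, and a constant daily rate fits poorly with reactions that cluster around an infusion.

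It can also be said that exposure-adjusted rates in an analysis plan would deal with unequal stays. For the in-hospital period they could; they cannot supply events after discharge.

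**Conclusion.** The point holds as a gap between claim and data collection. Adverse events are evaluated over each patient's stay, that window closes before an assessment the protocol already plans, and the safety hypothesis is not restricted to match. This rests on the text alone.

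Its size depends on length of stay, which is not stated: over the assumed 5 to 30 days, roughly half to 85% of the time to the post-discharge assessment carries no routine adverse-event enquiry. A bias between arms is a possibility rather than a finding. It would be near a ratio of 0.7 under the assumed rates and stays, and nil with equal stays or with events confined to the infusion. Given the exploratory status of safety, this is an inexpensive improvement and not a flaw in the main comparison.

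**What to change.** In section 2.5, collect adverse events over a fixed window from first administration, the same in both arms, for example through day 28. At the assessment 28 days after discharge, ask about any adverse event since discharge and record the onset date, so that events can be assigned to the window. Report reactions during administration separately from later events.

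If the window is to stay at discharge, limit the claim in section 2.6 to in-hospital tolerability.

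The cost is a few questions at an existing contact, a form page and slightly more data entry. The version is dated 29 June 2023 and the study dates run from August 2022 to December 2023, so participants already past their post-discharge contact will have in-hospital data only. The report should state this and give the numbers by arm.

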# Old Civil Hospital of Guadalajara "FRAY ANTONIO MAYOR"

Teaching Subdirector  
Research Coordination

## 2.6 HYPOTHESIS

Our hypothesis is that intravenous iron dextran repletion during the treatment of acute kidney injury will improve renal function parameters, iron deficiency, anemia, and also that it will be safe compared to placebo.

## 2. DESIGN OF THE STUDY

Randomized placebo-controlled clinical trial, randomization method in blocks of 5 by frequency of occurrence. In patients with acute kidney injury, they will be randomized to receive the administration of intravenous iron dextran in a single exhibition according to the Mg provided by the Virizzi formula compared to placebo.

The sample size determined 55 patients per group, with a standard deviation of 1.5.

$$n = [(Z_{\alpha/2} + Z_{\beta})^2 \times \{2(\sigma)^2\}] / (\mu_1 - \mu_2)^2$$
$$n = [(1.96 + 0.84)^2 \times \{2(1.5)^2\}] / (10.8 - 10)^2$$
$$n = 55,125$$

n = sample size required in each group  $\mu_1 - \mu_2 =$   
clinically significant difference = 0.8 or = standard  
deviation = 1.5

$Z_{\alpha/2}$ : 1.96

$Z_{\beta}$ : 0.84

Version 2.0, 29 June 2023

Effect of intravenous iron repletion on renal function in patients with iron deficiency and acute kidney injury, clinical trial. June 2023, HCG/CEI-1232/22

[name] [contact], [name] GUADALAJARA, JAL

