## Old Civil Hospital of Guadalajara "FRAY ANTONIO MAYOR"

Teaching Subdirectorato  
Research Coordination

all	94	placebo	2
all	95	placebo	2
all	96	placebo	2
all	97	placebo	2
all	98	Dextran Iron	1
all	99	Dextran Iron	1
all	100	placebo	2
all	101	Dextran Iron	1
all	102	placebo	2
all	103	Dextran Iron	1
all	104	Dextran Iron	1
all	105	placebo	2
all	106	placebo	2
all	107	placebo	2
all	108	Dextran Iron	1
all	109	placebo	2
all	110	Dextran Iron	1
all	111	Dextran Iron	1
all	112	placebo	2
all	113	Dextran Iron	1
all	114	Dextran Iron	1
all	115	placebo	2
all	116	placebo	2
all	117	Dextran Iron	1
all	118	Dextran Iron	1
all	119	placebo	2
all	120	placebo	2

Version 2.0, 29 June 2023

, and members of the nephrology staff, blinded to the allocation groups, administered the drugs to each patient every day.

All patients will have a detailed medical history and physical examination. Complete blood count, serum creatinine, serum urea, serum urea nitrogen, serum electrolytes, and blood test parameters were measured daily.

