## 4.2 VARIABLES UNDER STUDY

Exposure variable is the administration of iron dextran in an infusion bolus as a loading strategy.  
Dependent variables will be the value of renal function by eGFR, hemoglobin, iron deficiency, renal function and safety parameters.

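### The protocol gives the iron dextran as one single administration in one place and as a drug given every day in another

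*Protocol*

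**What the plan says.** The Protocol describes how the study drug is given in three places.

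- **Section 2, Design of the study (opening paragraph):** patients are randomized to "intravenous iron dextran in a single exhibition according to the Mg provided by the Virizzi formula", compared with placebo. The amount comes from a formula and is given once.
- **Section 2, text after the randomization list:** "members of the nephrology staff, blinded to the allocation groups", "administered the drugs to each patient every day". The beginning of this sentence is missing from the text at hand.
- **Section 4.2, Variables under study:** "Exposure variable is the administration of iron dextran in an infusion bolus as a loading strategy".

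Two other daily activities are stated separately. On laboratory tests, the paragraph after the administration sentence says that "serum electrolytes, and blood test parameters were measured daily". On safety, the exploratory objectives in section 2.5 place adverse-event checks during "drug administration and during hospitalization frequently every 24 hours by the nephrology staff".

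**The concern.** The statement in the design section and the statement after the randomization list cannot both describe what a patient receives, unless every patient is treated on one day only. The protocol tests one intervention against placebo, so the number of administrations is part of what defines the trial treatment.

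Two things are at stake.

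- **Safety.** The drug is a parenteral iron repletion dose, given to patients with acute kidney injury. Staff following the daily sentence literally would repeat or divide an amount that the design section gives once. The hypothesis in section 2.6 includes safety, so the exposure behind any safety statement has to be known.
- **Interpretation.** Ferritin, transferrin saturation and hemoglobin are secondary outcomes in section 2.5, and all three depend on how much iron was received. From this text a reader cannot tell which exposure the results would describe. The placebo has to follow the same schedule as the iron, so the blinding of the staff who give it also depends on which regimen applies.

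Adverse-event observation is not affected. It is set for the administration itself and for each 24 hours in hospital under either reading.

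**Working it through.** **Step 1. The statements side by side.**

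| Place in the protocol | What is given | How often |
|---|---|---|
| Section 2, opening paragraph | Formula-calculated amount of iron dextran, or placebo | Once |
| Section 4.2 | Infusion bolus, as a loading dose | Number not given; fits once |
| Section 2, after the randomization list | The drugs, to each patient, by blinded staff | Every day |

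The only study drugs that the protocol names are iron dextran and placebo, so the third row must refer to them.

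**Step 2. Can the daily phrase mean something else?**

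- *Laboratory tests.* These have their own sentence in the next paragraph, with their own frequency.
- *Safety checks.* These are in section 2.5, with their own frequency.
- *Staff being on duty each day.* The phrase is attached to giving drugs to each patient, not to staffing. If staffing was meant, the sentence does not say so.

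The words that survive contain a subject, a verb, an object, a recipient and a frequency. The plain reading is daily administration.

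**Step 3. Does anything reconcile the two?** Nothing in the protocol text divides the calculated amount over days, follows one active dose with daily placebo, or limits the number of days. The schedule of activities (section 5.1) is an attachment that is not shown.

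**Step 4. What each reading delivers.** Let D be a patient's calculated amount and k the number of treatment days. The protocol gives no value for k.

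| Reading | Infusions per patient | Total amount |
|---|---|---|
| Single dose | 1 | D |
| Daily, full amount repeated | k | k × D |
| Daily, amount divided | k | D, as D/k per day |

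At the planned size, the single-dose reading gives 2 × 55 × 1 = 110 infusions, 55 of iron and 55 of placebo. Under either daily reading the count exceeds 110 as soon as any patient is treated for more than one day. Total iron changes only if the full amount is repeated. Without k and a daily amount, no multiple can be stated.

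**Step 5. Is the sample size affected?** The protocol's own figure reproduces: (1.96 + 0.84)² × 2 × 1.5² / (10.8 − 10)² = 7.84 × 4.5 / 0.64 = 55.125 per group. Dosing frequency does not enter the formula, so the planned number does not depend on which statement is right.

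**The case against.** The strongest reply is that the conflict rests on a damaged sentence in a rough translation. The sentence resumes mid-clause after the randomization list, and its lost opening might have qualified it. The regimen is fixed where one would look for it, in the opening of the design section, and section 4.2 agrees. The daily sentence carries no dose and no number of days, so it could not be carried out as a regimen on its own. On this view it is a loose phrase about who gave the drug and whether they were blinded. The unseen schedule may also settle the matter.

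Part of this stands. A lost qualifier cannot be ruled out, which limits confidence to medium. The agreement between the opening of section 2 and section 4.2 makes the daily sentence the likelier error. The safety concern is conditional on someone acting on that sentence.

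It does not remove the contradiction. The surviving clause is complete enough to state a frequency of administration, and the other daily activities are accounted for elsewhere. A schedule could show which statement is right, but two incompatible statements would remain in the body of the protocol. Nor is this a detail that can be left to an analysis plan, because the number of doses defines the intervention.

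One further point bears on the remedy. The daily sentence is in the past tense, and version 2.0 is dated June 2023, inside the trial period of August 2022 to December 2023. It may therefore describe what was being done, so practice should be checked before either statement is corrected.

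**Conclusion.** The concern holds. The protocol states two incompatible dosing frequencies for its only active treatment and does not reconcile them. It should be fixed.

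The consequence is an undefined exposure: one administration per patient (110 infusions at the planned size) against an unspecified larger number. The total iron given would also differ if the full amount were repeated. There is no effect on the sample size, and none on adverse-event observation. No effect on the primary kidney-event endpoint has been shown or is claimed.

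The conclusion rests on two assumptions: that the missing opening of the daily sentence did not change its meaning, and that the drugs it refers to are the two study treatments. Confidence is medium because of the first.

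**What to change.** 1. **Establish from the treatment records how many administrations patients received.** Doses may already have been given when this version was issued, so this comes first.
2. **If dosing was single, as is likelier,** reword the sentence after the randomization list to say that blinded nephrology staff give one infusion, of the formula-calculated total amount of iron dextran or of placebo, once per patient.
3. **If repeated or divided dosing was intended,** amend the opening of section 2 and section 4.2 to state the number of days and the amount per day, on the same schedule for iron and placebo.
4. **Whichever applies,** make the schedule of activities agree with it. In the results, report the number of administrations and the total amount received per patient, by arm.

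In the likelier case the text change is one sentence. The additional work is retrieving administration data from patients' treatment records, and the protocol does not say how these are kept.
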